4.6 Unscheduled Visit

The investigator may see a subject for an unscheduled study visit at any time it is, in the investigator's opinion, necessary.

At unscheduled visits, the investigator or designee will perform the following procedures:

- 1. Query the subject in a non-directive manner about any changes in her/his health since the previous visit and report all AEs as appropriate
- 2. Query the subject about any changes in her/his concomitant therapies since the previous visit and report changes as appropriate
- 3. Review the study instructions with the subject
- 4. Schedule the next study visit.

Complete other study procedures that are, in the investigator's opinion, appropriate for the visit. Detailed instructions for documenting unscheduled visits will be included in the CRF guidelines.

4.7 Lost to Follow-up

A subject who appears to be unavailable for scheduled visits and is unable to be contacted by the study site will be considered lost to follow-up.

The following actions must be taken if a subject repeatedly fails to return to the study site for a required study visit:

- The investigator or designee must attempt to contact the subject and reschedule the missed visit as soon as possible and counsel the subject on the importance of maintaining the assigned visit schedule and ascertain whether or not the subject wishes to and/or should continue in the study.
- Before a subject is deemed lost to follow up, the investigator or designee must make every effort to regain contact with the subject (where possible, 3 telephone calls and, if necessary, a certified letter to the subject's last known mailing address or local equivalent methods). These contact attempts should be documented in the subject's medical record.
- Should the subject continue to be unreachable, she/he will be considered to have withdrawn from the study.

4.8 Subject discontinuation from the study

Subjects will be informed that they are free to withdraw from the study at any time and for any reason.

The investigator may remove a subject from the study if, in the investigator's opinion, it is not in the best interest of the subject to continue the study. The investigator must remove a subject from the study if the subject experiences:

- A Serious Adverse Event the investigator defines as related to the study medication, regardless of the intensity of the event
- A non-serious adverse event the investigator defines as related to study medication that has a severity of severe and requires treatment to resolve.

Examples of other reasons subjects may be discontinued from the study are a change in compliance with an inclusion or exclusion criterion, occurrence of AEs, occurrence of pregnancy or use of a prohibited therapy. Notification of discontinuation will immediately (within 24 hours) be made to the NFlection study monitor.

All withdrawn subjects with ongoing AEs will be followed as appropriate.

The study may be discontinued at the discretion of NFlection. Some examples of reasons for

discontinuation are the occurrence of the following:

- Increased frequency, severity or duration of known AEs
- Medical, regulatory or ethical reasons affecting the continued performance of the study
- Difficulties in the recruitment of subjects.

4.9 Replacement of subjects

Subject enrollment will continue until approximately 56 subjects have been randomized. Subjects who are randomized and do not complete the study will not be replaced.

4.10 Subject instructions

At Visit 1, an investigational center staff member will dispense a Subject Instruction sheet to each subject.

During the entire duration of the study subjects must:

- Continue to use her/his routine cleansers and cosmetics
- Not apply any non-study topical products to any Target cNF within 18 hours prior to a study visit
- Avoid exposing each Target cNF to excessive natural (e.g., sunlight) or artificial (e.g., tanning beds) ultraviolet radiation and use her/his routine sunscreen if excessive exposure cannot be avoided
- Bring the subject instruction sheet to every visit.

During the 4-week treatment period, subjects must:

- Apply the study medication to each Target cNF as directed, once daily, with 24 (±6) hours between applications
- Not apply the study medication to any open wounds or obviously infected skin
- For Visits 3 and 4 do not apply the study medication within 18 hours prior to the visit
- Prior to Visit 5 perform the study medication application 24 (±6) hours prior to the visit
- Not wash or submerge a Target cNF Tumor for at least 6 hours after a study medication application
- Not apply any topical products to a Target cNF for at least 6 hours after a study medication application
- Not allow anyone else to use your study medication
- Keep the study medication away from children
- Store the study medication at room temperature
- Bring all study medication tubes to every visit
- Bring the subject instruction sheet to every visit.

4.11 Previous and Concomitant Therapies

4.11.1 Previous therapies

At Visit 1, the investigator or designee will question the subject to ensure they have not used any excluded therapies.

4.11.2 Concomitant Therapies

Concomitant therapies are any new or existing therapy received from Visit 1 until discharge from the study.

Concomitant therapies include drug (*e.g.*, prescription, over-the-counter) and non-drug (*e.g.*, chiropractic, physical therapy, energy-based treatments) therapies. Subjects will refrain from receipt of any therapy in compliance with the inclusion/exclusion criteria. Subjects should refrain from changing the use of any concomitant therapies during the study.

All new or modified concomitant therapies used during the study must be recorded.

Any new or modified concomitant therapy must be considered to determine if it is related to an AE. An AE must be reported unless the therapy is modified for non-medical reasons (e.g., health insurance purposes), it is for prophylaxis (e.g., vaccinations), it is for the Visit 5 excision of, or post-excision management of the Study cNF Tumors following the investigator's standard of care.

4.11.3 Prohibited therapies

Subjects must not use any systemic therapy for cNF and must not use any topical cNF therapy on the Untreated cNF Tumor and must not use any topical cNF therapy other than the study medication, on any Target cNF Tumor.

During this study, subjects are prohibited from using therapies listed in the exclusion criteria. The investigator should notify the NFlection Medical Monitor immediately (within 24 hours) if any prohibited therapies are required to ensure subject safety.

Starting at Visit 2 subjects must avoid applying any topical product to any Target cNF Tumor for at least 6 hours after any study medication application.

4.12 Study Medications

The study medications are faint yellow, water clear gels and are indistinguishable in physical appearance. Study medications must be maintained in a secure area with limited access under appropriately controlled and monitored storage conditions at each investigational center.

4.12.1 Study medication identity

Study Medication Information					
Name	NFX-179 Gel	NFX-179 Gel	NFX-179 Gel	NFX-179 Gel	
	0.50%	0.15%	0.05%	Vehicle	
Manufacturer	MedPharm Limited				
	[name]				
	[name]				
Active ingredient	2-((2-fluoro-				
	hydroxyethoxy)-1-methyl-1 H -pyrrolo[2,3- b]			None	
	pyridine-3-carboxamide				
Active	0.50%	0.15%	0.05%	0%	
concentration	0.3070	0.1370	0.0370	070	
Storage conditions	59°F to 77°F (15°C to 25°C)				

The investigator or designee must confirm appropriate storage temperature was maintained during shipment for all study medication received and any discrepancies must be reported to NFlection and resolved before the study medication is dispensed.

4.12.2 Study medication packaging and labeling

The study medications will be packaged in identical appearing white plastic tubes that each contain 30 grams of study medication.

One Subject Kit that contains 2 tubes of study medication will be prepared for each subject.

Subject Kits will be labeled with a two-part, three-panel label. One part of the label remains affixed to the Subject Kit and the second part, a two-panel tear-off, is separated when the Subject Kit is first dispensed to the subject.

The affixed label part and the first panel of the tear-off label part show at least the following:

- Subject Kit number (Subject Kit number is also the randomization number)
- Protocol number
- Space to enter the SI
- Space to enter the date randomized
- Storage conditions
- NFlection information.

The second panel of the tear-off part is a blinded label (*e.g.*, scratch-off panel or equivalent) which when opened identifies the study medication in the Subject Kit. The blinded label should be opened only in a medical emergency.

Each study medication tube will be labeled with a one-part label that remains attached to the tube and shows at least the following:

- Subject Kit number
- Protocol number
- Tube number
- Space to enter the SI
- Space to enter the date dispensed
- Directions for use
- Investigational drug warning

4.12.3 Method of study medication assignment

Prior to the study start NFlection, or a designated third party, will generate a list of randomization numbers that will be provided to the assigned vendor for study medication labeling. The randomization number is also the Subject Kit number.

The randomization list will be stored with access limited to the appropriate personnel for the study medication labeling. The randomization list will be made available as appropriate to unblind the database.

4.12.4 Subject randomization

At Visit 2, the investigator will determine the subject's eligibility for randomization to study medication. To be eligible for randomization the subject must:

- Continue to fulfill all the inclusion criteria and none of the exclusion criteria
- If a Woman of Childbearing Potential (WOCBP), has a negative urine pregnancy test result at Visit 1 and Visit 2
- Have clinical laboratory test results for all measured analytes at Visit 1 and all results are either within the range of normal for the laboratory or, any abnormal results, are defined as Not Clinically Relevant (NCR) by the investigator
- Have Visit 1 ECG results that are defined as Normal.

The investigator or designee will assign study medication to eligible subjects by selecting the Subject Kits in chronological sequence in ascending numerical order starting with the lowest available Subject Kit number. The investigator will not omit or reuse any Subject Kit number.

4.12.5 Dispensing and collecting study medication

The study medication must be dispensed only to study subjects, only at investigational centers specified on the Form FDA 1572 (or its equivalent) and only by authorized personnel as required by applicable regulations and guidelines.

At Visit 2, after a subject is randomized, locate the Subject Kit with the lowest available number and complete the label.

Next locate the unused study medication tube with the lowest available number and complete the label. Weigh the study medication tube. Dispense one study medication tube to the subject for use in the first study medication application.

The subject must bring all dispensed study medication tubes with them to all visits.

At Visits 3 and 4, examine the study medication tubes dispensed to the subject, collect any tube that contains no useable study medication, weigh the tube and dispense a new tube, if required, following the instructions above.

At Visit 5, collect all study medication tubes from the subject and weigh each tube.30 grams (1

tube) of study medication tube is enough to complete the study medication applications for the duration of the study.

The investigational center staff member should make every effort to obtain all dispensed and unused study medication. Two documented telephone contacts followed by a registered letter to the subject are adequate follow-up efforts. If these efforts fail, the reason for the failure must be noted on the appropriate line of the study medication inventory CRF.

All unused and un-dispensed study medication should be held for inspection by NFlection's study monitor. Upon completion of the study all study medication will be returned to NFlection or a designated third party by the monitor using a traceable method.

4.12.6 Weighing study medication

An investigational center staff member will weigh each study medication tube when dispensed using the provided scale (or equivalent). The study medication container weight must be reported in grams (g) to the nearest 0.1g.

An investigational center staff member will weigh each study medication tube when returned. Study medication tubes that are examined and not collected from the subject because they contain useable study medication do not need to be weighed.

The study medication tube weights must be noted on the appropriate CRF.

The scale used to weigh the study medication tubes must be calibrated, according to the instructions provided for the scale, and the calibration documented, each day the scale is used, prior to use. Any scale that does not pass the calibration test must not be used to weigh the study medication.

4.12.7 Route of Administration, frequency and treatment period

The study medications are applied topically to each Target cNF Tumor, once daily for 28 days.

4.12.8 Study medication application

The study medications are for external, topical use on each Target cNF Tumor only and on the appropriate study subject only.

To perform a study medication application the subject should:

- Wash her/his hands before starting the application
- Avoid applying the study medication any open wounds or obviously infected skin
- Apply an amount of the assigned study medication sufficient to cover each Target cNF with a thin layer of the medication
- Gently rub in the study medication until no visible accumulation is evident
- Wash her/his hands after completing the application

The subject must apply study medication to the entire area of each Target cNF Tumor limiting exposure to the un-affected skin surrounding the tumor.

At Visit 2, an investigational center staff member will instruct the subject on the proper application technique. The staff member will observe the subject's study medication application to ensure proper application technique and record the time the subject completes the application to the last Target cNF Tumor as the Application Completion Time. The staff member will monitor the subject for adverse events for at least 20 minutes after the Application Completion Time. The subjects are to continue QD application of the assigned study medication to each Target cNF Tumor for 4 weeks with 24 (±6) hours between applications.

At Visit 5, the study medication application will be performed by the subject as part of the visit procedures at the investigational center. Record the time the subject completes the application to the last Target cNF Tumor as the Application Completion Time. The study medication tubes will be collected after the application at this visit.

For Visits 3 and 4 subjects should not apply the study medication within 18 hours prior to the study visit.

Prior to Visit 5 subjects must be instructed to perform the study medication application 24 (±6) hours prior to the visit.

After completing a study medication application, a subject should not:

- Wash or submerse any Target cNF Tumor for at least 6 hours
- Apply any topical products (*e.g.*, cosmetics, emollient/moisturizer, sunscreens) to any Target cNF Tumor for at least 6 hours.

4.12.9 Dose Modification

Subjects should not modify the study medication application procedure or frequency. All application modifications must be reported on the appropriate CRF page.

If any significant study medication intolerance or safety issue occurs, after consulting with the NFlection's Medical Monitor, the investigator or designee may direct the subject to reduce the study medication application frequency. If the subject cannot perform QD applications to all Target cNF Tumors for more than 4 consecutive days, the subject must be removed from the study.

4.12.10 Accountability

The investigator or designee will maintain an accurate record of the receipt of the study medications as shipped by NFlection or designee, including the date received and the condition of the study medications. One copy of this receipt will be returned to NFlection when the contents of the study medication shipment have been verified and one copy maintained in the study file. In addition, an accurate study medication disposition record will be kept, specifying the amount dispensed to each subject and the date of dispensing. This inventory record will be available for inspection at any time. At the completion of the study, the original inventory record will be available for review by NFlection upon request.

4.12.11 Return and disposition of study medication

At the completion of the study, all unused study medication will be returned to NFlection or designee for disposal per NFlection's or designee's written instructions.

4.13 Blinding

4.13.1 Verification of blinding

Blinding of the study medications is important for validity of this study. This study uses a double-blind design. The study medications are indistinguishable in appearance, packaging and labeling.

4.13.2 Unblinding the study medication

Blinding is important for validity of this study; however, the blind may be broken in the event of a medical emergency in which knowledge of the study medication identity is critical to the management of the subject's course of treatment. Before breaking the blind, the investigator should determine that the information is necessary (*i.e.*, that it will alter the subject's immediate course of treatment). In many cases, particularly when the emergency is clearly not study medication-related, the problem may be effectively managed by assuming that the subject is receiving active study medication without the need for unblinding.

If deemed necessary to break the blind for a study subject, attempt to contact the NFlection Medical Monitor to obtain concurrence. If it is not possible to contact the Medical Monitor beforehand, contact her/him as soon as possible after breaking the blind for a subject.

To identify a subject's study medication, locate the second panel of the Subject Kit tear-off label attached to the subject's CRF and follow the unblinding instructions on the label. Record the date of unblinding, the reason for unblinding and the initials of the investigational center staff member who performed the unblinding in the subject's CRF.

Any subject whose blind has been broken must be discharged from the study.

4.14 Study medication adherence

Adherence with the study medication application frequency will be monitored by questioning the subject regarding adherence at each visit and by measuring the weight of the study medication tubes when dispensed to the subject and when collected from the subject.

4.15 Other study supplies

In addition to the equipment and supplies provided for procedures, such as blood sampling, ultrasound measures and photography, NFlection, or designee, will provide the following items to each investigational center prior to the initiation of subject enrollment:

- Rulers for measuring each Study cNF Tumor
- Scales for weighing the study medication tubes
- Supplies for tissue excision processing and storage.

5 STUDY VISITS AND PROCEDURES

5.1 Schedule of Events

Visit	1 Screening	2 Randomization	3, 4 Treatment	5 End of treatment	6 Excision wound care	7 End of study	Protocol section
Day	-28 to 0	1	8, 15	29	36-50	57	1
Informed consent	X						11.3
Subject identifier (SI)	X						4.3
Inclusion/exclusion criteria	X	X					4.2
Demographics	X						6.3.1
Medical history	X	X					6.1.4
Physical examination	X						6.1.4
Vital signs	X	X		X		X	6.1.6
Clinical laboratory samples	X	X		X			6.1.2
Electrocardiogram (ECG)	X	X		X			6.1.8
Study/Target cNF Tumor location identification	X	X	X	X			5.3
Study/Target cNF Tumor dimensions	X	X		X			6.2.1
Local tolerability assessment (LTA)		X	X	X			6.1.3
Physician's Tumor Assessment (PTA)		X		X			6.2.4
Subject's Self-Assessment (SSA)		X		X			6.2.3
Ultrasound (select sites)		X		X			6.2.2
Photography	X	X		X			6.3.4
Study cNF Tumor excision				X			6.3.3
Excision wound care					X		6.3.3
Pharmacokinetic samples (select sites)		X		X			6.3.2
Urine pregnancy test	X	X		X			6.1.7
Screening	←						5.2.1
Randomization		X					4.12.4
Dispense/collect/weigh study medication		X	X	X			4.12.5/ 4.12.6
Once-daily (QD) application		-					4.12.8
No treatment follow-up					-		5.2.4
Subject instructions	X	X	X	X	X		4.10
Concomitant therapies	X	X	X	X	X	X	4.11.2
Adverse events		X	X	X	X	X	7

5.2 Study Visits

A written, signed informed consent form (ICF) must be obtained from each subject prior to performing any study related procedures and/or evaluations.

For Visits 3 and 4 subjects should not apply the study medication within 18 hours prior to a study visit.

Prior to Visit 5 subjects must be instructed to perform the study medication application 24 (±6) hours prior to Visit 5.

5.2.1 *Visit 1/Day -28 to 0 (Screening)*

At this visit, the investigator or designee will:

- 1. Review and explain the nature of the study to the subject, obtain the subject's signature on the appropriate approved ICF and Health Insurance Portability and Accountability Act (HIPAA) authorization and provide a signed and dated copy to the subject
- 2. Assign a Subject Identifier to the subject
- 3. Confirm the subject meets all inclusion criteria and no exclusion criteria
- 4. Collect demographic and medical history information
- 5. Report concomitant therapies information
- 6. Conduct a physical examination
- 7. Measure vital signs
- 8. Perform an ECG
- 9. Collect samples for clinical laboratory tests
- 10. Perform a urine pregnancy test for women of childbearing potential (WOCBP)
- 11. Identify 6 Study cNF Tumors (i.e., 5 Target cNF Tumors and 1 Untreated cNF Tumor)
- 12. Measure the dimensions of each of the 6 Study cNF Tumor
- 13. Take standardized color photographs of each of the 6 Study cNF Tumor
- 14. Review the study instructions with the subject and dispense a Subject Instruction Sheet
- 15. Schedule Visit 2 (Day 1) within 28 days.

5.2.2 Visit 2/Day 1 (Randomization; start of QD treatment)

This visit must occur within 28 days after Visit 1.

Subsequent study visit dates must be scheduled based on the date of this visit.

This visit may not occur until the investigator reviews the subject's Visit 1 clinical laboratory test results and ECG results.

At this visit, the investigator or designee will perform the following procedures PRIOR TO

RANDOMIZATION:

- 1. Query the subject in a non-directive manner about any changes in her/his health since the previous visit and report any changes as medical history or report as an AE as appropriate
- 2. Query the subject about any changes in her/his concomitant therapies since the previous visit and report changes as appropriate
- 3. Confirm the subject continues to fulfill all the inclusion criteria and none of the exclusion criteria
- 4. Confirm the subject has followed all study instructions
- 5. Perform a urine pregnancy test for WOCBP
- 6. Confirm the location of each Target cNF Tumor
- 7. Measure the dimensions of each Target cNF Tumor
- 8. Confirm subject is eligible for randomization, discharge subjects who are not eligible from the study.

For subjects eligible for randomization, the investigator or designee will perform the following procedures: `

- 1. Have the subject perform a pre-application Local Tolerability Assessment (LTA) of the symptoms for each Target cNF Tumor
- 2. Have the subject perform a Subject's Self-Assessment (SSA) for each Target cNF Tumor
- 3. The investigator will perform a pre-application LTA of the signs for each Target cNF Tumor
- 4. Perform a Physician's Tumor Assessment (PTA) for each Target cNF Tumor
- 5. Take standardized color photographs of each Target cNF Tumor
- 6. At select sites only: Perform an ultrasound of each Target cNF Tumor
- 7. Measure vital signs
- 8. Perform an ECG
- 9. Collect samples for clinical laboratory tests
- 10. Randomize eligible subjects
- 11. Weigh and dispense study medication
- 12. At select sites only: Collect a blood sample for PK analysis prior to the first study medication application
- 13. An investigational center staff member must:
 - Instruct the subject on the proper study medication application technique
 - Observe the subject's first study medication application to each Target cNF Tumor and record the Application Completion Time
 - Monitor the subject for at least 20 minutes after the Application Completion Time
- 14. Have the subject perform a post-application LTA of the symptoms for each Target cNF Tumor 10 (±4) minutes after the Application Completion Time
- 15. The investigator will perform a post-application LTA of the signs for each Target cNF Tumor 20 (±4) minutes after the Application Completion Time
- 16. Review the study instructions with the subject
- 17. Schedule Visit 3.

Date: 24-JUL-2020 Page 40 of 78 Supersedes: NEW

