The third and fourth secondary objectives are to determine the clinical efficacy of NFX-179 Gel defined as the change from baseline in the Subject's Self-Assessment grade and Physician's Tumor Assessment grade, separately, after 28 days of treatment. Appropriate mixed-model ANCOVAs will be used to compare, for each treated tumor, change from baseline grade between treatment groups, with treatment as the independent factor, baseline value as the covariate, and subject as the repeated factor. ANCOVA models will also be performed on the subject level after first calculating the within-subject mean values across treated tumors. In addition, for each assessment dichotomized analyses will be conducted on the proportion of tumors achieving a grade of Clear, and also the proportion of tumors achieving a grade of either Clear or Almost Clear, after 28 days of treatment. Treatment groups will be compared to vehicle using appropriate mixed-model logistic regression, as well as a Chisquare analysis of within-subject averaged results across tumors.

Safety Analyses:

Subjects will be assessed for the occurrence of new and ongoing AEs. Descriptions of AEs will include the dates of onset and resolution (if resolved), maximum severity, seriousness, and action taken regarding the study drug, corrective treatment, outcome, and investigator's assessment of causality. All AEs will be recorded and classified using terminology from the Medical Dictionary for Regulatory Activities (MedDRA). All reported treatment-emergent AEs (TEAEs), defined as any AE with an onset on or after the date of first study drug application, will be summarized by treatment group, the number of subjects reporting TEAEs, system organ class, preferred term, severity, and relationship to study drug. When summarizing TEAEs by severity or relationship to study drug, each subject will be counted only once within a system organ class or a preferred term using the event with the greatest severity or causality, respectively, within each category. All reported serious adverse events (SAEs) will be summarized by treatment group, the number of subjects

reporting SAEs, system organ class, preferred term, severity, and relationship to study drug.

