6.1.8 Electrocardiogram

A 12-lead ECG will be performed by a qualified investigational center staff member at the Visits 1, 2 (prior to randomization) and 5.

The ECGs must be obtained using a 12-lead ECG with a 10mm/mV amplitude, at 25mm/sec and 5-10 second duration. To ensure a steady heart rate the subject must rest quietly in the supine position for at least 5 minutes prior to performing the ECG.

The following parameter, at a minimum, will be determined:

- Heart rate
- RR interval
- PR interval
- QRS interval
- QT and QTc.

A normal ECG is defined as:

- QTc ≤450msec for males and ≤460msec for females (use of the ECG algorithm is acceptable for this purpose)
- Heart rate that is \geq 50 and \leq 100 beats/minutes
- The tracing must not show any:
 - o Rhythm disturbance other than a benign sinus dysrhythmia
 - Conduction disturbance including First Degree A-V Block (PR >200msec) and preexcitation (PR <120msec)
 - o Acute or chronic signs of ischemia.

Variations such as minor ST changes (*i.e.*, <0.5mm depression) and early re-polarization are considered normal.

The ECG results must be interpreted by a qualified health professional, the evaluator, and the interpretation reported either directly on the tracing or in a separate report. The evaluator and the investigator or designee may be the same person.

The investigator or a designee must review the ECG reports in a timely manner and in all cases prior to the next study visit. If an ECG result is defined as abnormal by the evaluator the investigator or designee should define the abnormality as CR or NCR. The investigator will record this information directly on the ECG tracing/report and date and initial the tracing/report.

The subject must not be randomized if the Visit 1 ECG is, in the evaluator's opinion, abnormal, regardless of the clinical relevance.

The investigator must report ECG results that are BOTH abnormal AND CR as medical history if found prior to the first study medication application or as an AE if found after the first study medication application begins.

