7.1 Definitions

7.1.1 Adverse Event (AE)

An AE is any untoward medical occurrence in a patient or clinical investigation subject administered a pharmaceutical product and which does not necessarily have a causal relationship with this treatment. An AE can therefore be any unfavorable and unintended sign or symptom associated with the use of an investigational product (including an abnormal laboratory finding), whether or not related to the investigational product.

Thus, any new, CR worsening of an existing sign, symptom or disease, should be considered an AE.

Worsening of the any Target cNF assessment should be reported as an AE only if the use of the study medication is interrupted or discontinued or other therapy is required to manage the event.

Every new episode or clinically relevant worsening of a chronic condition (*e.g.*, headaches, allergies, depression, and hypertension) should be reported as a separate AE, even if the condition is reported in the subject's medical history.

The investigator should, when certain, report a diagnosis rather than the signs, symptoms or clinically relevant abnormal laboratory values associated with the AE. Otherwise, signs, symptoms or abnormal laboratory values may be used to describe the AE.

An abnormality discovered (*e.g.*, clinically relevant laboratory abnormalities), prior to the first study medication application, should be reported as medical history, not as an AE.

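### The Visit 2 ECG is taken before randomization but need not be read until after dosing, so an abnormal and clinically relevant Day 1 tracing does not have to stop the first application

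*Combined protocol and SAP*

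**What the plan says.** **Order of events.** Section 5.2.2 sets out Visit 2 in two lists. The first precedes randomization and ends at step 8: "Confirm subject is eligible for randomization, discharge subjects who are not eligible from the study". The second is for subjects who have passed that step. In it the ECG is step 8, randomization step 10, dispensing step 11 and the observed first application step 13. Section 6.1.8 also places this ECG before randomization.

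**Reading the tracing.** Section 6.1.8 asks for interpretation by a qualified health professional, and adds: "The evaluator and the investigator or designee may be the same person". On the deadline, it says that whoever carries out the site's review "must review the ECG reports in a timely manner and in all cases prior to the next study visit".

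**Bars to randomization.** Section 6.1.8 says "The subject must not be randomized if the Visit 1 ECG is" judged abnormal, whether or not the abnormality is clinically relevant. Section 4.12.4 asks for a normal Visit 1 ECG. Section 5.2.2 does not let Visit 2 take place until the Visit 1 laboratory and ECG results have been reviewed. No sentence sets an ECG condition for Visit 2.

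**Recording.** Under 6.1.8 an abnormal and clinically relevant ECG is reported "as medical history if found prior to the first study medication application"; the other branch is to report it "as an AE if found after the first study medication application begins". Section 7.1.1 applies the same test to any abnormality discovered "prior to the first study medication application, should be reported as medical history, not as an AE". In the synopsis (Safety Analyses) a treatment-emergent AE (TEAE) is "defined as any AE with an onset on or after the date of first study drug application".

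**The concern.** A tracing obtained before randomization can protect the subject only if someone looks at it before the drug goes on. The plan collects it in time but does not require that look. It also leaves an asymmetry. At Visit 1 any abnormality stops randomization, but up to 28 days later a tracing that is both abnormal and clinically relevant carries no explicit bar. Where the plan wants a Visit 2 condition it writes one: the pregnancy test must be negative at both visits (4.12.4, 6.1.7).

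Two things are at stake. The first is the subject's safety: section 8.3.4 describes a first-in-human study with an unknown human risk profile. The second is the AE data, since safety and AEs are primary endpoints (section 2). The same pre-dose finding is filed differently according to when it is read.

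**Working it through.** The plan states no figure on this point, so the check is mainly a comparison of texts, followed by some short arithmetic.

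**1. Can dosing come before reading?**

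| Question | Source | Answer for the Visit 2 ECG |
|---|---|---|
| When is it taken? | 5.2.2, second list, step 8; 6.1.8 | Before randomization, after eligibility is confirmed |
| Is there a reading or recheck step before step 10 or step 13? | 5.2.2 | None |
| When must it be reviewed? | 6.1.8 | Timely, and at the latest before Visit 3 |
| Does an explicit ECG bar apply? | 4.12.4, 5.2.2, 6.1.8 | No; each names Visit 1 |

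So the text allows dosing before reading.

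**2. Outer limit of exposure.** Section 5.2.3 puts Visit 3 at 7 ± 4 days after Visit 2, that is 7 − 4 = 3 to 7 + 4 = 11 days. At one application a day from Day 1, at most 3 to 11 applications could precede the review deadline. This is a worst case, because review must also be timely.

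**3. How a late-read finding is recorded.**
- It was present before dosing but found after the first application, so 6.1.8 makes it an AE. Read in time, it would have been medical history.
- Whether it is also a TEAE depends on its onset date. The synopsis definition works by date, so an onset dated to the Day 1 tracing, or to the later reading, qualifies. An onset dated before Day 1 does not.

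**4. Size of the reporting effect, per subject so classified.**
- Arm of 12 (synopsis, 48 subjects): 1/12 = 8.3%.
- Arm of 14 (section 4.1, 56 subjects): 56/4 = 14, and 1/14 = 7.1%.

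These percentages apply to the row for that ECG term. The count of subjects with any TEAE rises only if the subject has no other TEAE.

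**5. How often?** The documents give no rate *p* for an abnormal and clinically relevant Visit 2 ECG after a normal Visit 1 ECG. The values below are assumptions. The expected number of such tracings in the whole study is *n* × *p*.

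| Assumed *p* | *n* = 48 | *n* = 56 |
|---|---|---|
| 0.5% | 0.24 | 0.28 |
| 1% | 0.48 | 0.56 |
| 2% | 0.96 | 1.12 |

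Only tracings read after dosing matter, and that share is unknown. Given *p*, these counts are therefore upper bounds.

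**The case against.** **It is a design choice.** The second list in 5.2.2 is a baseline set, and the synopsis assesses ECGs partly for change from baseline. The gate is at Visit 1, it is strict, and it must be cleared before Visit 2. This stands as an account of the structure, and it is why the point is an improvement and not the repair of a contradiction. But a baseline tracing can still be read before dosing.

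**Other safeguards exist.** Review must be timely, step 10 speaks only of eligible subjects, section 4.12.4 requires that no exclusion criterion is met at Visit 2, and exclusions 5 and 8 let the investigator stop for unacceptable risk. All of this is true, and nothing suggests that late reading is intended. Apart from the timeliness wording, though, these safeguards work only once the tracing has been read, and no text requires that before dosing.

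**The effect on TEAEs is easily overstated.** A reader might infer that every abnormality read late adds a TEAE subject to its arm. The documents do not support that. AE start dates are recorded (6.1.1), so an investigator could date a pre-existing abnormality before Day 1. Section 8.3.4 has a separate pre-treatment AE category. Section 8.3.1 leaves analysis detail to a SAP. A subject with another TEAE is already in the any-TEAE count. This objection stands in full.

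**Why single out the ECG?** Visit 2 laboratory samples follow the same pattern, but the synopsis refers to a central laboratory, so same-day results cannot be assumed. Visit 2 vital signs (step 7) are available at once and also have no explicit bar. That observation is fair. It is a reason to consider vital signs too, not a reason to leave the ECG unread.

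**Conclusion.** The gap is real but small. The text allows a subject with an abnormal and clinically relevant Day 1 ECG to be randomized and dosed before the tracing is read. A finding read late would then be an AE instead of medical history, and could become a TEAE if its onset is dated Day 1 or later. The reporting effect is one subject in that ECG term's row, 8.3% of 12 or 7.1% of 14.

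Expected impact is low. A normal Visit 1 ECG within the previous 28 days is required, section 3.2 expects extremely low systemic absorption, and section 7.1.4 does not list cardiac events among those of special interest. Under the assumed rates of 0.5% to 2%, about one such tracing or fewer is expected in the whole study, before allowing for those read in time.

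The reading of the text is firm; the frequency is unknown. The check uses the revised protocol of 24 July 2020. The later amendment supplied changes only section 8.3.3, and the text of Amendment 2 is not among the documents. This is a cheap improvement of low priority.

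**What to change.** - **Sections 5.2.2 and 6.1.8:** require the Visit 2 ECG to be interpreted by the qualified evaluator and reviewed by the investigator or designee before step 10.
- **Section 4.12.4:** add that a subject whose Visit 2 ECG is abnormal and clinically relevant is not randomized. A tracing that is normal, or abnormal but not clinically relevant, may proceed, as under the existing Visit 1 laboratory rule.
- **Unchanged:** the Visit 1 requirement of a normal ECG stays as the stricter screening gate. This leaves two ECG standards on purpose, one for screening and one for a same-day safety check. The order of the other Visit 2 procedures does not change.

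**Cost.** Wording in three sections and no new procedure, since the ECG is already taken before randomization. Subjects wait a short time on Day 1, and a few may be discharged that day. Where the investigator is not the evaluator, the site needs a qualified reader reachable on Day 1, and the wait may be longer. Section 6.1.8 accepts the machine algorithm for QTc only, so rhythm, conduction and ischemia still need that reader.
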